## FLOW CHART

### FLOW CHART PART 1 (ROSUVASTATIN)

Period	Visit	Day	Planned time (relative to drug administration) [h:min]	Approximate clock time of actual day [h:min]	Event and comment	Safety laboratory 	PK blood, Rosuvastatin	PK blood, BI 1323495	12-lead ECG	Vital signs (BP, PR)	Questioning for AEs and concomitant therapy 			
SCR	1	-21 to -1			Screening (SCR) 	X A			X	X				
1/2 (two identical periods separated by a wash-out of at least 7 days)	2/3	1	-2:00	06:00	Admission to trial site 	X B,2,3	X 	X 	X 	X 	X 			
			-0:30	07:30	Standardised breakfast									
			0:00	08:00	Drug administration									
			0:30	08:30					X 					
			1:00	09:00				X	X 					
			2:00	10:00	240 mL fluid intake			X	X 					
			3:00	11:00				X	X 					
			3:30	11:30				X						
			4:00	12:00	240 mL fluid intake			X	X 					
			4:30	12:30				X						
			5:00	13:00	Lunch 			X	X 				X	
			5:30	13:30				X						
			6:00	14:00				X	X 					
			7:00	15:00				X						
			8:00	16:00	Snack (voluntary) 			X	X 					
			10:00	18:00				X						
			11:00	19:00	Dinner									
			12:00	20:00				X	X 				X	
			2	24:00	08:00	Breakfast (voluntary) 			X B	X	X 	X	X	X
				28:30	12:30	Lunch (voluntary) 								X
32:00	16:00	Snack (voluntary)												
34:00	18:00	Discharge from trial site					X				X			
3	47:00	07:00	Ambulatory visit			X				X				
4	71:00	07:00	Ambulatory visit			X				X				
5	95:00	07:00	Ambulatory visit			X				X				
FU	4	8 to 15			End of trial (EoTrial) examination 	X C			X	X	X			

- Subject must be informed and written informed consent obtained prior to starting any screening procedures. Screening procedures include physical examination, check of vital signs, ECG, safety laboratory (including drug screening), [REDACTED] demographics (including determination of body height and weight, smoking status and alcohol history), relevant medical history, concomitant therapy and review of inclusion/exclusion criteria. [REDACTED]
- The time is approximate; the procedure is to be performed and completed within the 3 h prior to drug administration.
- Includes urine drug screening and alcohol breath test
- If several actions are indicated at the same time, the intake of meals will be the last action.
- Letters A, B, and C define different sets of safety laboratory examinations (for details refer to Section 5.2.3)
- At the end of trial visit the EoTrial examination includes physical examination, vital signs, ECG, safety laboratory, recording of AEs and concomitant therapies.
- AEs and concomitant therapies will be recorded throughout the trial, but will be specifically asked for at the times indicated in the Flow Chart above.
- Period with administration of test treatment (rosuvastatin + BI 1323495) only

**FLOW CHART PART 2 (DABIGATRAN)**

[figure not shown]
[figure not shown]
[figure not shown]
Period	Visit	Day	Planned time (relative to drug administration) [h:min]	Approximate clock time of actual day [h:min]	Event and comment	Safety laboratory 	PK blood , Dabigatran	PK blood , BI 1323495	12-lead ECG	Vital signs (BP, PR)	Questioning for AEs and concomitant therapy 			
SCR	1	-21 to -1			Screening (SCR) 	x A			x	x				
1/2 (two identical periods separated by a wash-out of at least 7 days)	2/3	1	-2:00	06:00	Admission to trial site 	x B,2,3	x 	x 	x 	x 	x 			
			-0:30	07:30	Standardised breakfast									
			0:00	08:00	Drug administration									
			0:30	08:30			x	x 						
			1:00	09:00			x	x 						
			1:30	09:30			x							
			2:00	10:00	240 mL fluid intake		x	x 						
			2:30	10:30			x							
			3:00	11:00			x	x 						
			3:30	11:30			x							
			4:00	12:00	240 mL fluid intake		x	x 						
			5:00	13:00	Lunch 		x	x 					x	
			6:00	14:00			x	x 						
			8:00	16:00	Snack (voluntary) 		x	x 						
			10:00	18:00			x							
			11:00	19:00	Dinner									
			12:00	20:00			x	x 					x	
		2	24:00	08:00	Breakfast (voluntary) 	x B	x	x 	x	x	x			
			28:30	12:30	Lunch (voluntary) 							x		
			32:00	16:00	Snack (voluntary)									
			34:00	18:00	Discharge from trial site		x						x	
		3	47:00	07:00	Ambulatory visit		x				x			
			71:00	07:00	Ambulatory visit		x					x		
FU	4	8 to 15			End of trial (EoTrial) examination 	x C			x	x	x			

1. Subject must be informed and written informed consent obtained prior to starting any screening procedures. Screening procedures include physical examination, check of vital signs, ECG, safety laboratory (including drug screening and faecal occult blood test), [REDACTED] demographics (including determination of body height and weight, smoking status and alcohol history), relevant medical history, concomitant therapy and review of inclusion/exclusion criteria. [REDACTED]
2. The time is approximate; the procedure is to be performed and completed within the 3 h prior to drug administration.
3. Includes urine drug screening and alcohol breath test
4. If several actions are indicated at the same time, the intake of meals will be the last action.
5. Letters A, B, and C define different sets of safety laboratory examinations (for details refer to Section 5.2.3)
6. At the end of trial visit the EoTrial examination includes physical examination, vital signs, ECG, safety laboratory (including faecal occult blood test), recording of AEs and concomitant therapies.
7. AEs and concomitant therapies will be recorded throughout the trial, but will be specifically asked for at the times indicated in the Flow Chart above.
8. Period with administration of test treatment (dabigatran + BI 1323495) only

## ABBREVIATIONS

ADME	Absorption, distribution, metabolism, and excretion
AE	Adverse event
AESI	Adverse events of special interest
ANOVA	Analysis of variance
AUC 0-∞	Area under the concentration-time curve of the analyte in plasma over the time interval from 0 extrapolated to infinity

AUC 0-tz	Area under the concentration-time curve of the analyte in plasma over the time interval from 0 to the last quantifiable data point
AUC 0-24	Area under the concentration-time curve of the analyte in plasma over the time interval from 0 to 24 hours after drug administration
BA	Bioavailability
BCRP	Breast cancer resistance protein
BI	Boehringer Ingelheim
BMI	Body mass index (weight divided by height squared)
BP	Blood pressure
CA	Competent authority
CI	Confidence interval

C max	Maximum measured concentration of the analyte in plasma
CF	Cystic fibrosis
CFTR	Cystic fibrosis transmembrane conductance regulator
COPD	Chronic obstructive pulmonary disease

CRF	Case Report Form, paper or electronic (sometimes referred to as 'eCRF')
CTP	Clinical trial protocol
CTR	Clinical trial report
CYP	Cytochrome P450 system
DILI	Drug induced liver injury
ECG	Electrocardiogram
eCRF	Electronic case report form
eDC	Electronic data capture
EDTA	Ethylenediaminetetraacetic acid
EoTrial	End of trial

EudraCT	European Clinical Trials Database
FOB	Faecal occult blood
FU	Follow-up
GCP	Good Clinical Practice
gCV	Geometric coefficient of variation
gMean	Geometric mean
HMG-CoA	Hydroxymethylglutaryl coenzyme A
HPC	Human Pharmacology Centre
IB	Investigator's brochure
IC	Inhibitory concentration
IEC	Independent Ethics Committee
IRB	Institutional Review Board
ISF	Investigator site file

MDA	Methylenedioxyamphetamine
MDMA	Methylenedioxymethamphetamine
MedDRA	Medical Dictionary for Regulatory Activities

[figure not shown]
OATP	Organic anion transporting polypeptide
P-gp	P-glycoprotein
PK	Pharmacokinetic(s)
PKS	Pharmacokinetic set
PP	Polypropylene
PR	Pulse rate
QT	Time between start of the Q-wave and the end of the T-wave in an electrocardiogram
QTc	QT interval corrected for heart rate using the method of Fridericia (QTcF) or Bazett (QTcB)
R	Reference treatment
REP	Residual effect period
SAE	Serious adverse event
SCR	Screening
SmPC	Summary of Product Characteristics
SOP	Standard operating procedure
SRD	Single-rising dose
T	Test treatment

$t_{\max}$	Time from (last) dosing to the maximum measured concentration of the analyte in plasma
TS	Treated set
$t_z$	Time of last measurable concentration of the analyte in plasma
TSAP	Trial statistical analysis plan

ULN Upper limit of normal

[figure not shown]
XTC Ecstasy

## 1. INTRODUCTION

BI 1323495 has been characterised to be an inhibitor of P-glycoprotein (P-gp), Breast cancer resistance protein (BCRP) and of the Organic anion transporting polypeptide (OATP) 1B1 *in-vitro*. This trial will be performed to investigate whether, and to which extent, BI 1323495 is also *in-vivo* an inhibitor of these drug transporters.

### 1.1 MEDICAL BACKGROUND

## 1.2 DRUG PROFILE

### 1.2.1 BI 1323495

For a detailed description of the BI 1323495 profile, please refer to the current Investigator's Brochure [[c21238478-02](#)].

#### Clinical experience

At the time of preparing this trial protocol, three Phase I studies with administration of single doses of BI 1323495 to healthy male volunteers have been completed, trials 1405-0001 (first-in-man trial), 1405-0007 (relative BA/food effect), and 1405-0009 (drug interaction with itraconazole).

In the single rising dose (SRD) trial 1405-0001, single-dose treatment with up to 600 mg BI 1323495 or placebo was safe and well tolerated. There was no relationship between the occurrence of AEs and dose. Three AEs in subjects receiving BI 1323495 were judged as moderate in intensity, all other AEs were classified as mild. No severe or serious AEs were

reported. The most frequently reported treatment-emergent AE was headache, reported for 6 out of 48 subjects (12.5%) receiving BI 1323495 and 2 out of 15 subjects (13.3%) receiving placebo. The next-most frequently reported treatment-emergent AEs were fatigue and diarrhea, each reported for 2 out of 48 subjects (4.2%) receiving BI 1323495. In one subject receiving 300 mg BI 1323495, a mild (<2-fold ULN) and transient elevation of ALT and GLDH was reported.

For further details on safety and tolerability as well as on pharmacokinetics and biomarker data of the SRD trial refer to the IB ([c21238478-02](#)).

In the food effect trial 1405-0007, a randomised 2-way crossover study to compare the relative bioavailability of a single dose of [REDACTED] BI 1323495 [REDACTED] administered in the fasted state versus fed state (high-fat), [REDACTED]

Treatment-emergent AEs were reported for 5 out of the 12 treated subjects (41.7%). Adverse events were reported for 3 out of 12 subjects (25.0%) in the BI 1323495 fasted treatment period and for 2 out of 11 subjects (18.2%) in the BI 1323495 fed treatment period. No subjects were reported with AEs in both treatment periods.

Infections and infestations occurred in 2 of the 12 subjects (16.7%): influenza in 1 subject in the BI 1323495 fasted treatment period, and otitis externa in 1 subject in the BI 1323495 fed treatment period. Headache was reported in 2 of the 12 subjects (16.7%), one in each treatment period. Mouth injury was reported in 1 of the 12 subjects (8.3%) in the BI 1323495 fasted treatment period. The only investigator-defined drug-related AE was mild headache reported for 1 subject [[c27223001-01](#)].

Trial 1405-0009, a two-period fixed sequence study in healthy male subjects [REDACTED] [REDACTED] investigated the effects of multiple doses of itraconazole – a strong CYP3A4 and P-gp inhibitor - on the relative bioavailability of a single dose of [REDACTED] BI 1323495. The clinical part has been completed and data are currently being evaluated.

Treatment-emergent AEs were reported for 6 out of the 14 treated subjects (42.9%). Investigator defined drug-related AEs were reported for 3 subjects (21.4%), all of them mild or moderate diarrhea under treatment with itraconazole alone or itraconazole + BI 1323495. No relevant changes in vital signs, ECG, or laboratory parameters were reported.

In summary, single doses of BI 1323495 investigated so far in clinical trials with healthy subjects were safe and well tolerated.

### 1.2.2 Rosuvastatin

Rosuvastatin is an HMG-CoA reductase inhibitor indicated for treatment of hypercholesterolemia and for prophylaxis of cardiovascular events. Inhibition of HMG-CoA decreases hepatic cholesterol production, which, in turn, stimulates hepatocellular uptake of low-density lipoproteins. In therapy, the initial rosuvastatin dose is 5-10 mg once daily. The daily dose may be increased to up to 40 mg [R19-3033].

After oral administration, maximal rosuvastatin plasma concentrations are reached at ~5 h. Oral bioavailability is ~20%, plasma protein binding is ~90%, and volume of distribution is ~134 L. The liver is a principal compartment of distribution, with hepatocellular uptake being mediated mainly by OATP1B1 and, to a lesser degree, by OATP1B3. Elimination is mainly via the feces and to a lesser degree, via urine (principally via renal tubular secretion), with a  $t_{1/2}$  of 19 h [R19-3033, P14-07833].

Adverse reactions to rosuvastatin are normally mild and transient. Myalgia and myopathy with concomitant increase of creatine kinase, and, in rare cases, rhabdomyolysis have been observed during rosuvastatin therapy. Moreover, as for other HMG-CoA reductase inhibitors, a dose-dependent increase of liver transaminases may be observed [R19-3033].

For a more detailed description of the rosuvastatin profile, please refer to the current SmPC for Crestor® 10 mg tablets [R19-3033].

### 1.2.3 Dabigatran

Dabigatran etexilate is a small molecule prodrug which does not exhibit any pharmacological activity. After oral administration, dabigatran etexilate is rapidly absorbed and converted to dabigatran by esterase-catalysed hydrolysis in plasma and in the liver. Dabigatran is a potent, competitive, reversible direct thrombin inhibitor and is the main active principle in plasma. Since thrombin (serine protease) enables the conversion of fibrinogen into fibrin during the coagulation cascade, its inhibition prevents the development of thrombus. Dabigatran inhibits free thrombin, fibrin-bound thrombin and thrombin-induced platelet aggregation.

Dabigatran is indicated for primary prevention of venous thromboembolic events in adult patients who have undergone elective total hip replacement surgery or total knee replacement surgery, and for the prevention of ischaemic stroke in patients with atrial fibrillation. The recommended daily dose for primary prevention of venous thromboembolism in orthopaedic surgery is 220 mg with an initial dose of 110 mg prior to the surgery. In patients with moderately impaired renal clearance (30-50 mL/min) the dose should be reduced to 150 mg daily (1 capsule of 75 mg bid) [R18-3151].

The absolute bioavailability of dabigatran following oral administration was approximately 6.5%. After oral administration in healthy volunteers, the pharmacokinetic profile of dabigatran in plasma is characterized by a rapid increase in plasma concentrations with  $C_{max}$  attained within 0.5 and 2.0 hours post administration, a bi-exponential distribution phase and a terminal elimination half-life of about 11 hours in healthy elderly subjects. Food does not affect the bioavailability of dabigatran etexilate but delays the time to peak plasma concentrations by 2 hours. Neither dabigatran etexilate nor dabigatran interacts with CYPs. No drug-drug interactions based on CYP dependent pathways have been identified. Dabigatran etexilate but not the active moiety, dabigatran, is a substrate of the efflux

transporter P-glycoprotein (P-gp). Accordingly, the bioavailability of dabigatran is increased when P-gp inhibitors such as verapamil, quinidine, amiodarone, dronedarone or ketoconazole are co-administered [[R18-3151](#)].

Overall, more than 1000 healthy volunteers have been included in phase I trials with dabigatran etexilate.

Adverse events were few, mild, and included primarily hematoma at the venipuncture site or need for prolonged compression for hemostasis on venous catheter removal at higher doses. Major bleedings were not observed in the Phase I trials. At the highest dose of dabigatran etexilate studied in humans, 400 mg three times daily as oral solution, 6 of 8 subjects reported mild bleeding such as hematoma or prolonged bleeding at a venous puncture site, or gingival bleeding [[U00-1856](#)].

For a more detailed description of the dabigatran profile, please refer to the current SmPC for Pradaxa® 75 mg hard capsules [[R19-3343](#)].

#### 1.2.4 Residual Effect Period

The Residual Effect Period (REP) of BI 1323495, rosuvastatin, and dabigatran, i.e. the period after the last dose with measurable drug levels and/or pharmacodynamic effects still likely to be present, will be defined as 7 days for each of the 3 products.

### 1.3 RATIONALE FOR PERFORMING THE TRIAL

Based on *in-vitro* data BI 1323495 is an inhibitor of P-gp, BCRP, OATP1B1. This trial will be performed to test the inhibitory effect of BI 1323495 on these drug transporters *in-vivo*. Rosuvastatin will be used as a model substrate of BCRP and OATP1B1 (trial Part 1) and dabigatran as a model substrate of P-gp (Part 2).

### 1.4 BENEFIT - RISK ASSESSMENT

Participation in this clinical trial is without any (therapeutic) benefit for healthy subjects. Their participation, however, is of major importance for the clinical development of BI 1323495. Subjects are exposed to risks of study procedures and risks related to the exposure to the trial medication.

### Procedure-related risks

[figure not shown]
The use of an indwelling venous catheter or venepuncture for e.g. blood sampling may result in mild bruising, and in rare cases, in transient inflammation of the wall of the vein, or nerve injury, potentially resulting in paraesthesia, reduced sensibility, and/or pain for an indefinite period, as well as in feeling of lightheadedness or in syncope.

The total volume of blood withdrawn per subject during the entire study will not exceed the volume of a normal blood donation (500 mL). No health-related risk to healthy subjects is expected from withdrawal of this volume of blood.

### Drug-related risks

Although rare, a potential for drug-induced liver injury (DILI) is under constant surveillance by sponsors and regulators. Therefore, this trial requires timely detection, evaluation, and follow-up of laboratory alterations in selected liver laboratory parameters to ensure subjects' safety; see also Section [5.2.6.1.4](#), adverse events of special interest.

*BI 1323495*

In the SRD, food effect, and itraconazole drug interaction trial, single dose administration of up to 600 mg BI 1323495 was well tolerated, with no clinically relevant changes in any safety laboratory parameter, ECG, and vital signs observed (ref. Section [1.2.1](#)). The occurrence of AEs did not appear to be related to BI 1323495 plasma exposure.

As with all drugs, the potential for hypersensitivity and allergic reactions has to be taken into consideration when BI 1323495 is administered.

#### *Rosuvastatin*

A single dose of 10 mg rosuvastatin has been well tolerated by healthy subjects in several clinical trials [[c03246006-01](#), [c08983809-01](#), [c13060859-01](#)].

The combined administration of 10 mg rosuvastatin with the OATP1B1/1B3-inhibitor rifampin in trial 352.2100 increased the rosuvastatin exposure from 6.8 to 77 nmol/L ( $C_{max}$ ) and from 94 to 321 nmol/L\*h ( $AUC_{0-\infty}$ ). This increase was well tolerated by healthy subjects [[c23988236-01](#)]. Comparable effects of rifampin on rosuvastatin exposure have been also described by Lai et al [[R17-1790](#)] and by Prueksaritanont et al [[R15-4771](#)].

Rifampin is a strong and well characterised inhibitor of OATP1B1/1B3 and is therefore recommended for testing OATP inhibition [[R18-0241](#)]. Considering this, it is assumed that the potential effect of BI 1323495 on the OATP-substrate rosuvastatin does not exceed the strong effect of rifampin on rosuvastatin exposure described above. Based on the good tolerability observed in trial 352.2100, no undue risk to healthy subjects is expected from the combined administration of 10 mg rosuvastatin and BI 1323495 in this trial.

#### *Dabigatran*

[figure not shown]
In trial 1160.60 a single dose of 600 mg dabigatran etexilate was well tolerated by healthy subjects [[U06-1614-01](#)]. Taking into account the dose-proportional kinetics of dabigatran, the well tolerated single dose of 600 mg provides a safety margin of 4 to the therapeutic dose of 150 mg daily and of 8 to the dose being used in Part 2 of this trial (75 mg).

Dabigatran etexilate is a sensitive substrate of intestinal P-gp. The effect of several P-gp inhibitors has been tested in healthy subjects. The strongest effects have been seen with a single dose of verapamil given 1 hour before dabigatran intake (2.8 fold increase of dabigatran  $C_{max}$ ) and with multiple doses of ketoconazole (2.5 fold increase of dabigatran  $C_{max}$  und AUC) [R19-3343]. The observed increase in dabigatran exposure has been well tolerated by healthy subjects, which is in line with the described safety margin of 4 at a dose of 150 mg, that has not been exceeded by any P-gp inhibitor.

No undue risk to healthy subjects is expected from the combined administration of 75 mg dabigatran etexilate and BI 1323495 in this trial.

#### Risk mitigation and monitoring

- Careful selection of trial population with compound-specific exclusion criteria (see Section 3.3.3)
- Only healthy subjects will be included in this trial not requiring concomitant medications that could – in principle – trigger combined effects on the pharmacokinetics and / or safety of the investigational drugs.
- Although relevant alterations are not specifically expected, liver function tests including total and direct bilirubin, serum creatinine, urea, electrolyte levels, glomerular filtration rate, and blood coagulation parameters will be monitored as part of the standard safety laboratory assessments (see Section 5.2.3). Subjects with impaired liver, kidney or blood coagulation function will be excluded from participation in this trial. Furthermore, monitoring will be done for any signs of bleeding or bleeding-related adverse events.

- 
- Safety surveillance with close monitoring and in-house confinement up to at least 34 hours after drug administration

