#### 5.2.3 Safety laboratory parameters

For the assessment of laboratory parameters, blood and urine samples will be collected by the trial site at the times indicated in the Flow Chart after the subjects have fasted for at least 10 h. For retests, at the discretion of the investigator or designee, overnight fasting is not required.

The parameters that will be determined are listed in Tables [5.2.3: 1](#) and [5.2.3: 2](#). Reference ranges will be provided in the ISF, Section 10.

Manual differential white blood cell count or urine sediment examinations will only be performed if there is an abnormality in the automatic blood cell count or in the urinalysis, respectively.

Faecal occult blood testing, using an immunochemical test kit for hemoglobin, will be performed by the laboratory at the time points indicated in the [Flow Chart for Part 2](#).

Table 5.2.3: 1 Routine laboratory tests

Functional lab group	BI test name [comment/abbreviation]	A 	B 	C 
Haematology	Haematocrit	X	X	X
	Haemoglobin	X	X	X
	Red Blood Cell Count/Erythrocytes	X	X	X
	White Blood Cells/Leucocytes	X	X	X
	Platelet Count/Thrombocytes (quant)	X	X	X
Automatic WBC differential, relative	Neutrophils/Leukocytes; Eosinophils/Leukocytes; Basophils/ Leukocytes; Monocytes/Leukocytes; Lymphocytes/Leukocytes	X	--	X
Automatic WBC differential, absolute	Neutrophil, absol.; Eosinophils, absol.; Basophils, absol.; Monocytes, absol.; Lymphocytes, absol.	X	--	X
Manual differential WBC (if automatic differential WBC is abnormal)	Neut. Poly (segs); Neut. Poly (segs), absol.; Neutrophils Bands; Neutrophils Bands, absol.; Eosinophils/Leukocytes; Eosinophils, absol.; Basophils/ Leukocytes; Basophils, absol.; Monocytes/ Leukocytes; Monocytes, absol.; Lymphocytes/Leukocytes; Lymphocytes, absol.			
Coagulation	Activated Partial Thromboplastin Time	X	X	X
	Prothrombin time	X	X	X
	INR (International Normalization Ratio)	X	X	X
Enzymes	AST [Aspartate transaminase] /GOT, SGOT	X	X	X
	ALT [Alanine transaminase] /GPT, SGPT	X	X	X
	Alkaline Phosphatase	X	X	X
	Gamma-Glutamyl Transferase	X	X	X
	Creatine Kinase [CK]	X	X	X
	Creatine Kinase Isoenzyme MB [only if CK is elevated]	X	X	X
Hormones	Thyroid Stimulating Hormone	X	--	--
Substrates	Glucose (Plasma)	X	--	X
	Creatinine	X	X	X
	GFR/ CKD-EPI 	X	X	X
	Bilirubin, Total	X	--	X
	Bilirubin, Direct	X	--	X
	Protein, Total	X	--	X
	C-Reactive Protein (Quant)	X	--	X
Electrolytes	Sodium	X	--	X
	Potassium	X	--	X

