Urinalysis (Stix)	Urine Nitrite (qual)	X	X	X
	Urine Protein (qual)	X	X	X
	Urine Glucose (qual)	X	X	X
	Urine Ketone (qual)	X	X	X
	Urobilinogen (qual)	X	X	X
	Urine Bilirubin (qual)	X	X	X
	Urine RBC/Erythrocytes (qual)	X	X	X
	Urine WBC/Leucocytes (qual)	X	X	X
	Urine pH	X	X	X
Urine sediment (microscopic examination if erythrocytes, leukocytes nitrite or protein are abnormal in urine)	Only positive findings will be reported (for instance, the presence of sediment bacteria, casts in sediment, squamous epithelial cells, erythrocytes, leukocytes)			

 A: parameters to be determined at Visit 1 (screening examination)  
 B: parameters to be determined at Visit 2 and 3 (for study days and time points refer to [Flow Chart](#))  
 C: parameters to be determined at Visit 4 (end of trial examination)  
 Estimated glomerular filtration rate according to CKD-EPI formula ([R12-1392](#))

The tests listed in Table 5.2.3: 2 are exclusionary laboratory tests that may be repeated as required. The results will not be entered in the CRF/database and will not be reported in the CTR. Except for drug screening, it is planned to perform these tests during screening only. Drug screening will be performed at screening and prior to each treatment period.

Table 5.2.3: 2 Exclusionary laboratory tests

Functional lab group	Test name
Drug screening (urine)	Amphetamine/MDA Barbiturates Benzodiazepine Cannabis Cocaine Methadone Methamphetamines/MDMA/XTC Opiates Phencyclidine Tricyclic antidepressants
Infectious serology (blood)	Hepatitis B surface antigen (qualitative) Hepatitis B core antibody (qualitative) Hepatitis C antibodies (qualitative) HIV-1 and HIV-2 antibody (qualitative)

To encourage compliance with alcoholic restrictions, a breath alcohol test (e.g. Alco True M®, [REDACTED]) will be performed prior to each treatment period, and may be repeated at any time during the study at the discretion of an investigator or designee. The results will not be included in the CTR.

The laboratory tests listed in Tables 5.2.3: 1 and 5.2.3: 2 will be performed at [REDACTED], with the exception of drug screening tests. These tests will be performed at the trial site using AccuSign® DOA 10 test or comparable test systems.

Laboratory data will be transmitted electronically from the laboratory to the trial site.

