## 5.7 APPROPRIATENESS OF MEASUREMENTS

All measurements performed during this trial are standard measurements and will be performed in order to monitor subjects' safety and to determine pharmacokinetic parameters in an appropriate way. The scheduled measurements will allow monitoring of changes in vital signs, standard laboratory values, and ECG parameters that might occur as a result of administration of trial medication. The safety assessments are standard, are accepted for evaluation of safety and tolerability of an orally administered drug, and are widely used in clinical trials. The pharmacokinetic measurements outlined in Section [5.3](#) are generally used assessments of drug exposure.

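### Section 1.4 lists urea, electrolytes and bilirubin as monitored safety parameters, but Table 5.2.3: 1 never schedules urea and schedules the others only at screening and end of trial

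*Protocol*

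**What the plan says.** Protocol Section 1.4, under risk mitigation and monitoring, lists liver function tests including total and direct bilirubin. The same sentence continues with "serum creatinine, urea, electrolyte levels, glomerular filtration rate, and blood coagulation parameters will be monitored as part of the standard safety laboratory assessments" and points to Section 5.2.3 for the detail. It gives no visit, period or frequency.

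Section 5.2.3 is the operative list: "The parameters that will be determined are listed in Tables" 5.2.3: 1 and 5.2.3: 2. Table 5.2.3: 1 assigns each test to set A (screening), set B or set C (end of trial). Its footnote reads "B: parameters to be determined at Visit 2 and 3", so set B is the treatment-period panel. Both flow charts place set B before dosing and at 24 h in each period, and set C at Day 8 to 15.

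Protocol Section 5.7 adds a general assurance: "The scheduled measurements will allow monitoring of changes in vital signs, standard laboratory values", among others.

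SAP Section 6.1 ends the on-treatment phase at 0:00 h on day 7 after dosing, or at the next dose if that comes first. It presents laboratory tables by on-treatment phase. SAP Section 6.7 takes as baseline the last value before dosing in each period.

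**The concern.** Section 1.4 supports the benefit-risk conclusion put to the ethics committee and the authority, and that conclusion relies on the safety measures described there. A site works from Table 5.2.3: 1. If the table omits a parameter that Section 1.4 names, the site can follow the protocol exactly and still not collect it.

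Two further consequences concern the data. In a crossover, a laboratory change can be tied to test or reference only if it is measured within each period, and a single value after both treatments cannot separate them. Second, Sections 3.3.4.1 (criterion 5) and 5.2.6.1.4 both use a combined transaminase and total bilirubin threshold in one blood sample. A panel that has transaminases but no total bilirubin cannot show whether that threshold was met.

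**Working it through.** The plan gives no figure to reproduce. The check sets Section 1.4 against Table 5.2.3: 1 and the flow charts.

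**Laboratory occasions per subject** (both parts alike): 1 screening (set A) + 2 periods × 2 draws (set B, pre-dose and 24 h) + 1 end of trial (set C) = 6, of which 4 are in the treatment periods.

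**Parameters named in Section 1.4, by set:**

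| Parameter | A | B | C | Occasions of 6 | Treatment-period occasions of 4 |
|---|---|---|---|---|---|
| Urea | no | no | no | 0 | 0 |
| Sodium, potassium | yes | no | yes | 2 | 0 |
| Total and direct bilirubin | yes | no | yes | 2 | 0 |
| Creatinine, GFR | yes | yes | yes | 6 | 4 |
| aPTT, PT, INR | yes | yes | yes | 6 | 4 |
| AST, ALT (as liver function tests) | yes | yes | yes | 6 | 4 |

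The contrast is visible in two rows of the substrates block: "Creatinine X X X" against "Bilirubin, Total X -- X". Table 5.2.3: 2 holds only drug screening and infectious serology, so urea is not there either.

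**Whole trial:** 28 subjects × 6 = 168 planned occasions. Urea is planned at 0. Sodium, potassium and bilirubin are planned at 28 × 2 = 56, and at none of the 28 × 4 = 112 treatment-period draws.

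**On-treatment values.** I read the end-of-trial window, Day 8 to 15, as counted from the Period 2 dose, with dosing on Day 1. The earliest set C draw is then 7 days after that dose, and the on-treatment phase has closed at 0:00 h that day at the latest. For a subject who completes as planned, no scheduled post-dose sodium, potassium or bilirubin value is on treatment, for test or for reference.

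**Baseline.** Without these analytes in set B, the only scheduled pre-dose value for both periods is screening. With screening from Day -21, it can be 21 days old at the first dose and 21 + 7 = 28 days old at the second with the minimum wash-out (more with a longer one).

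**Hepatic-injury criterion.** One limb needs AST and/or ALT at 3-fold ULN or more with total bilirubin at 2-fold ULN or more in the same sample. Set B supplies AST and ALT but no total bilirubin; its urine stick gives only a qualitative urinary bilirubin. The other limb, transaminases at 10-fold ULN or more, can be assessed from set B.

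**The case against.** The strongest reply is that Section 1.4 promises monitoring but no schedule. Sodium, potassium and bilirubin are measured at screening and again after dosing at the end of trial, which fits the sentence as written. This stands: for these four analytes the documents do not contradict each other. A reader might infer that the stated electrolyte monitoring does not take place at all, and that would be wrong. The reply does not help urea, which has no occasion.

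The impact is also limited. Section 1.4 expects no particular change in these parameters, and the protocol reports no clinically relevant laboratory changes with single doses up to 600 mg. Renal function is followed by creatinine and GFR in every set. The investigator may order retests, must obtain transaminases and bilirubin if there are clinical signs of hepatic injury, and must follow up clinically relevant abnormal values. The SAP has a rule for unscheduled laboratory values. All of this stands, but none of it schedules a measurement.

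Two other inferences are tempting. One is that the gap is confined to urea and electrolytes; the bilirubin rows, named in the same sentence, show that it is not. The other is that exclusion criterion 21, which mentions hypokalaemia, requires potassium on dosing days. That criterion concerns a history of risk factors at entry. Potassium is measured at screening, and nothing in the documents calls for a dosing-day value.

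Finally, the table was read from a PDF, so a lost row cannot be fully excluded. The substrates and electrolytes blocks read as continuous, with no sign of redaction.

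**Conclusion.** The point holds in two parts. Urea is a direct contradiction: named as monitored in Section 1.4 and scheduled at 0 of 6 occasions. Sodium, potassium, and total and direct bilirubin are a gap in the schedule: 2 of 6 occasions and 0 of 4 in the treatment periods. For these the SAP's on-treatment laboratory tables would contain no scheduled post-dose value, and set B transaminases could not be judged against the same-sample bilirubin limb from scheduled results.

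This rests on the table being completely extracted, on the end-of-trial window counting from the Period 2 dose, and on subjects completing as planned. A subject who stops early could have the end-of-trial draw within the on-treatment phase.

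No primary or secondary endpoint is affected. The matter is what safety data are collected and whether the stated risk mitigation matches the schedule. It should be corrected, but it does not show that subjects' kidney or liver function goes unmonitored.

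**What to change.** Reconcile Section 1.4 with Table 5.2.3: 1. The documents do not show which passage is the intended one, so the choice is the sponsor's.

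- **Extend the table.** For example, add a urea row and include sodium, potassium, and total and direct bilirubin in set B at the draws already scheduled. With urea in all three sets this is at most 6 + 4 × 4 = 22 extra results per subject. No new laboratory time points are needed. The protocol gives no tube type or volume for the safety laboratory, so the site should confirm that the existing sample suffices.
- **Correct the text.** Remove urea from Section 1.4 and state which parameters are measured at which visits. This adds no laboratory work. The protocol should then say how the same-sample bilirubin limb is to be assessed at treatment-period draws. The SAP should state that screening serves as baseline for analytes outside set B, and that they have no scheduled on-treatment value.

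Either route is a short protocol amendment.
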